#### 12.8. Preplanned Hospitalizations or Procedures

During the study, if a subject has a hospitalization or procedure (e.g., elective surgery) that was scheduled prior to the subject entering the study (i.e., before the subject signed the ICF) for an event/condition that occurred before the study, the hospitalization is considered a therapeutic intervention and not the result of an SAE. However, if the event/condition worsens during the study, it must be reported as an AE or SAE (if the event/condition results in a serious outcome such as prolongation of hospitalization.)

## **13. STATISTICS**

The Statistical Analysis Plan (SAP) will provide comprehensive details on the statistical methods and sensitivity analyses for dealing with dropouts, planned for this study prior to database lock.

#### 13.1. Data Analysis

## **13.1.1** Analysis Populations

Safety Analysis Set (SAS) will include all subjects who received at least one dose of study drug and had at least one post dose safety assessment.

Per Protocol Set: The group of subjects who received at least one dose of study drug and who did not have any major protocol deviations.

## 13.1.2 Statistical Analysis Plan

A statistical analysis plan will outline the efficacy analysis and safety analysis prior to database lock.

#### **13.1.3** Sample Size Justification

No prior data are available on which to base assumptions for sample size/power considerations. The results of this pilot study will be used to design future studies, and the sample size of approximately 40 subjects is deemed to be appropriate for this purpose.

## 13.1.4 Safety Analysis

Safety analyses will be conducted on the Safety Analysis Set.

The incidence of treatment-emergent AEs (TEAEs, defined as AEs occurring from the time of first dose through 7 days after the last dose of study medication), SAEs and AEs leading to discontinuations will be summarized by treatment group. Incidence of TEAEs will also be summarized by severity (mild, moderate, or severe), as well as by relationship to treatment (not related, possibly related, or probably related) and by seriousness.

Changes from baseline in laboratory values will be summarized for continuous variables. Lab shift tables showing incidence of new or worsening clinically significant findings from baseline to the last visit will be displayed. Shift from baseline to the highest lab value, and from baseline to the lowest lab value will also be displayed.

Incidence of out-of-normal-range values and markedly abnormal change from baseline in laboratory safety test variables will be tabulated.

Changes in vital signs from baseline to each visit will be summarized by treatment groups.

#### **13.2.** Direct Access to Source Data/Documents

By signing this protocol, the PI agrees to conduct the study in an efficient and diligent manner and in conformance with this protocol; generally accepted standards of Good Clinical Practice (GCP); and all applicable federal, state, and local laws, rules and regulations relating to the conduct of the clinical study.

The PI also agrees to allow monitoring, audits, and regulatory agency inspection of study-related documents and procedures and provide for direct access to all study-related source data and documents.

The PI shall prepare and maintain complete and accurate study documentation in compliance with GCP standards and applicable federal, state, and local laws, rules, and regulations; and, for each subject participating in the study, provide all data, and upon completion or termination of the clinical study submit any other reports to the Sponsor, or its designee, as required by this protocol or as otherwise required pursuant to any agreement with the Sponsor.

Study documentation will be promptly and fully disclosed to the Sponsor, or its designee, by the PI upon request and shall also be made available at the PI's site upon request for inspection, copying, review, and audit at reasonable times by representatives of the Sponsor or any regulatory agencies. The PI agrees to promptly take any reasonable steps that are requested by the Sponsor, or its designee, as a result of an audit to address deficiencies in the study documentation and worksheets/CRFs.

The PI will promptly inform the Sponsor or its designee of any regulatory agency inspection conducted for this study.

Persons debarred from conducting or working on clinical studies by any court or regulatory agency will not be allowed to conduct or work on this Sponsor's studies. The PI will immediately disclose in writing to the Sponsor or its designee if any person who is involved in conducting the study is debarred, or if any proceeding for debarment is pending or, to the best of the Investigator's knowledge, threatened.

#### 13.3. Study Monitoring

Monitoring will include on-site monitoring to assure that the investigation is conducted according to protocol, to protect subject rights and safety, and to confirm data integrity and quality.

This study will be monitored through all phases of study conduct by the Sponsor or its representative. Monitoring will include personal visits and telephone communication to assure that the investigation is conducted according to protocol and in order to comply with guidelines of GCP. On-site review of CRFs will include a review of forms for completeness and clarity, and consistency with source documents available for each subject. Investigators will be required to store all source documents.

#### 13.4. Audits and Inspections

The PI and appropriate personnel may be periodically requested to attend meetings organized by the Sponsor or its designee to assure acceptable protocol execution. The study may be subject to audit by the Sponsor/designee or by regulatory authorities. If such an audit occurs, the PI must agree to allow access to required subject records. By signing this protocol, the Investigator grants permission to personnel from the Sponsor, its representatives, and appropriate regulatory authorities for on-site monitoring and auditing of all appropriate study documentation, as well as on-site review of the procedures employed in CRF generation, where clinically appropriate. The PI has to inform the Sponsor if he/she is approached for a regulatory audit.

## 13.5. Institutional Review Board (IRB)

Before initiation of the study, the PI must obtain approval of the research protocol, informed consent form (ICF), and any advertisement for subject recruitment from the IRB complying with the provisions specified in the Code of Federal Regulations (CFR) 21 Part 56 and applicable government regulations. A copy of written IRB approval of the protocol, ICF, and advertising (if applicable) must be provided to the Sponsor or their designee prior to initiation of the study.

## **13.6.** Study Documentation

By signing a copy of Form FDA 1572, the Investigator acknowledges that he/she has received a copy of the investigational drug brochure on MN-001 and assures the Sponsor that he/she will comply with the protocol and the provisions stated in Form FDA 1572. No changes in this protocol can be made without the Sponsor's written approval.

The Investigator will supply the Sponsor with the following:

- 1. Original, signed Form FDA 1572
- 2. Curricula vitae for all Investigators listed on Form FDA 1572
- 3. Copy of the Investigator's medical licensure/medical registration number
- 4. Signed protocol signature page
- 5. Signed IB signature page
- 6. Financial disclosure forms for all study staff listed on the FDA 1572.

# 14. QUALITY CONTROL AND QUALITY ASSURANCE

By signing this protocol, the Sponsor and Clinical Study Sites Principal Investigator agree to be responsible for implementing and maintaining quality control and quality assurance systems with written standard operating procedures (SOPs) reviewed and approved by the sponsor to ensure that the study is conducted and data are generated, documented, and reported in compliance with the protocol, accepted standards of GCP, and all applicable federal, state, and local laws, rules and regulations relating to the conduct of the clinical study.

# 15. ETHICS

#### 15.1. Ethics Review

Documented approval from the IRB will be obtained for all participating centers prior to clinical trial start, according to ICH (International Conference on Harmonisation) GCP, local laws, regulations and organization. When necessary, an extension, amendment or renewal of the CIRB approval must be obtained.

## **15.2.** Ethical Conduct of the Study

The procedures set out in this clinical trial protocol pertaining to the conduct, evaluation, and documentation of this clinical trial, are designed to ensure that the Sponsor and Principal Investigator abide by Good Clinical Practice Guidelines (GCP in the appropriate current version). The clinical trial will also be carried out in accordance with applicable local law(s) and regulation(s). This may include an inspection by representatives from MediciNova Inc. and/or Regulatory Authority representatives at any time. The PI must agree to the inspection of clinical trial-related records by MediciNova, Inc. representatives, and must allow representatives direct access to source documents.

## 15.3. Written Informed Consent

An information and consent form will be provided to the subject. The process of obtaining informed consent must be in accordance with applicable regulatory requirements, and must adhere to GCP and ethical principles in the Declaration of Helsinki. Written informed consent must be obtained and documented before any clinical trial-specific procedure takes place. Participation in the clinical trial and date of informed consent given by the subject must be documented in the subject files.

## 15.4. Confidentiality

#### **15.4.1.** Confidentiality of Data

By signing this protocol, the Investigator affirms to the Sponsor that information furnished to the Investigator by the Sponsor will be maintained in confidence and such information will be divulged to the IRB or similar or expert committee; affiliated institution; and employees only under an appropriate understanding of confidentiality with such board or committee, affiliated institution and employees.

# 16. DATA HANDLING AND RECORDKEEPING

#### 16.1. Review of Records

The results from Screening and data collected during the study will be recorded in the subject's CRF, which will be designed and provided by the sponsor or a designee. The Investigator will review all CRFs. The CRFs will be signed by the PI or a sub-Investigator who is listed on the Form FDA 1572 if the PI is unavailable. In order to maintain confidentiality, the subject will be identified only by his/her subject number and initials.

#### 16.2. Retention of Records

The PI must arrange for retention of study records at the site for at least two years after the New Drug Application (NDA) is approved or Investigational New Drug (IND) is withdrawn, as required by the US Food and Drug Administration (FDA) regulations, or in accordance with local and/or national requirements, whichever is longer. The PI should take measures to prevent accidental or premature destruction of these documents. Documents cannot be destroyed without written Sponsor authorization. The Sponsor will inform the PI when the destruction of documents is permitted.

# **17. ADMINISTRATIVE AND REGULATORY DETAILS**

#### 17.1. Protocol Amendments and Study Termination

All revisions and/or amendments to this protocol must be approved in writing from the Sponsor and the IRB, except where necessary to eliminate an apparent immediate hazard to a study subject.

#### 17.2. Discontinuation of the Study

The Sponsor reserves the right to discontinue the study at site(s) for safety or administrative reasons at any time. For example, a site that does not recruit at an acceptable rate may be discontinued. Should the study be terminated and/or the site closed for whatever reason, all documentation and study medication pertaining to the study must be returned to the Sponsor or its representative.

#### 17.3. Compliance with Financial Disclosure Requirements

By signing this protocol, the PI agrees to provide to the Sponsor accurate financial information to allow the Sponsor to submit complete and accurate certification and disclosure statements as required by the US FDA regulations (21 CFR Part 54). The PI further agrees to provide this information on a Financial Disclosure/Certification Form that is provided by MediciNova Inc. The Investigator will update this information if there are any relevant changes during the conduct of the study and for one year after completion of the study. This requirement also extends to sub-Investigators. The PI also consents to the transmission of this information to MediciNova Inc. for these purposes.

# **19. APPENDICES**

# Appendix 1: Laboratory Safety Tests for MN-001

Blood Chemistry Tests		
aspartate aminotransferase (AST)		
alanine aminotransferase (ALT)		
albumin		
alkaline phosphatase		
bicarbonate		
blood urea nitrogen		
calcium		
chloride		
creatinine		
creatine phosphokinase (CPK)		
gamma-glutamyl transferase		
phosphorous		
potassium		
sodium		
total bilirubin a		
total protein		
lactate dehydrogenase		
triglyceride		
serum cholesterol		
serum high-density lipoprotein cholesterol		
serum low-density lipoprotein cholesterol		
glucose		
Endocrine Tests		
serum beta-human chorionic gonadotropin (for females of childbearing potential)		
urine beta-human chorionic gonadotropin		
Hematology Tests		
white blood cell count		
white blood cell differential		
eosinophilic leukocyte count		
basophilic leukocyte count		
neutrophil count		
lymphocyte count		
monocyte count		
platelet count		
hemoglobin		
blood hematocrit		
red blood cell count		
red cell distribution width		
red blood cell indices:		
mean corpuscular volume		
mean corpuscular hemoglobin concentration		
mean corpuscular hemoglobin		
Coagulation Tests		
INR		
PT		
APTT		

Urinalysis Tests	
color	
appearance	
total ketones	
urobilinogen	
bilirubin	
red blood cells	
leukocyte esterase	
nitrite	
pН	
protein	
specific gravity	
glucose	
microscopic evaluation	b

a Bilirubin will be fractionated (direct serum bilirubin test/indirect serum bilirubin test) if elevated 2.0 times the upper limit of the normal range.

b Microscopic evaluation will be performed if dipstick analysis indicates the presence of any significant abnormality.

# **Appendix 3: Cholesterol Efflux Study Protocol**

## **Cholesterol Efflux Assay Protocol**

The procedure described below is for macrophage cell line J774.1. This procedure can also be used with macrophage cells derived from THP-1 monocytes, by addition of 100 nM phorbol 12-myristate 13-acetate (PMA) for 48 h.

# 1. Label Cells:

Grow J774.1 cells in RPMI 1640 media containing 10% FBS in cell culture flask till ~90% confluency (37°C incubator containing 5% CO2). Split cells under sterile conditions using basic cell culture techniques & plate approximately 1 x 105 J774.1 cells/well in a 96-well plate (white plate with clear bottom) using 100 2l media/well. Grow for 2 h in a 37°C incubator containing 5% CO2. After 2 hours, when the cells are attached to the plates, wash the cell monolayer with RPMI 1640 media (no serum added). Premix 50 2l of Labeling Reagent and 50 2l of Equilibration Buffer containing Reagent A and B/well just before use. Add 100 2l mix/well. Incubate the plate overnight (16 hrs.) in a 37°C incubator containing 5% CO2.

Notes:

a. To test the background fluorescence, add 100 2l of Equilibration Buffer containing Reagent A and B to the cell monolayer. Don't add labelling reagent to the background control well(s).

b. For accurate assay, we recommend each treatment and control to be performed in triplicates.

# 2. Treat Cells:

After 16 h, remove the Labeling Reagent. Wash the cells gently by adding 200 2l of RPMI media (no serum) to all the wells. Remove the media. Treat cells with desired cholesterol acceptors in RPMI media. If using human serum as cholesterol acceptor, pre-treat the serum with Serum Treatment Reagent. Add 2 parts of Serum Treatment Reagent to 5 parts of human serum (Ratio 2:5).

Incubate for 20 min. on ice. Centrifuge the mixture at 9,000 x g, for 10 min. at 4°C. Use the supernatant to treat the cells as desired and make up the volume to 100 2l by RPMI media. For Positive Control, add 20 2l of Positive Control & make up the volume to 100 2l by

RPMI media. For no treatment control, add 100 21 RPMI media (no serum) to no treatment control well(s). Incubate cells for 4-6 h. in a 37°C incubator containing 5% CO2.
## 3. Measurement:

At the end of incubation, transfer supernatant to a 96-well plate (white plate). Measure the fluorescence (Ex/Em = 482/515 nm). Solubilize the cell monolayer by adding 100 2l of Cell Lysis Buffer and shaking on a plate shaker for 30 min at room temperature. Pipette up and down to dissolve any cell debris. Measure the fluorescence (Ex/Em = 482/515 nm).

## 4. Calculations:

Cholesterol efflux of the treatments is calculated by dividing the fluorescence intensity of the media by total fluorescence intensity of the cell lysate of the same treatment & media. This value is multiplied by 100 to obtain % Cholesterol Efflux. Subtract %

Cholesterol Efflux obtained from no treatment control from the treatment groups to determine the final % Cholesterol Efflux.

Figure: Percentage (%) Cholesterol Efflux: J774.1 cells were labeled with the Labeling Media and treated with various cholesterol acceptors like Human Serum, HDL (50 2g) or Positive control known to cause cholesterol efflux. Cholesterol efflux is expressed as % efflux elicited by cells in 4h.

# 4 ABBREVIATIONS AND DEFINITIONS

### **ABBREVIATION**

AE	Adverse Event
ALP	Alkaline Phosphatase
ALT	Alanine Aminotransferase
$AUC_{0 \rightarrow t}$	Area Under the Concentration vs. Time
	Curve
AUC 0→∞	Area Under the Concentration Versus Time Curve, from Time 0 to Infinity
Bid	Twice Daily
Cmin	Minimum Concentration
C max	Maximum Concentration
Clast	Concentration at the time of the last measurable concentration
CRF	Case Report Form
CSS	Concentration Steady-State
ECG	Electrocardiogram
eCRF	Electronic Case Report Form
ER	Extended-Release
FDA	Food and Drug Administration
GCP	Good Clinical Practice
Н	Hour
ICF	Informed Consent Form
ICH	International Conference on Harmonization
IR	Intermediate-Release
IRB	Institutional/independent Review Board
MedDRA	Medical Dictionary for Regulatory Activities
PD	Pharmacodynamics
РК	Pharmacokinetics
QD	Once Daily
ОТ	Time Between the Beginning of the QRS Complex and the End of the T-
QI	Wave
QTcB	QT interval using Bazette's correction
QTcF	QT interval using Fridericia's correction
SAE	Serious Adverse Event
SD	Standard Deviation
SAP	Statistical Analysis Plan
t1/2	Terminal Elimination Half Life
t max	Time to Maximum Measured Concentration
Tid	Three Times Daily
λz	Terminal Elimination Rate Constant

### DEFINITIONS

Adverse Event	An adverse event (AE) is any untoward medical occurrence in a subject administered a pharmaceutical product, regardless of causality assessment.		
Full Analysis Set Population	Group of randomized subjects who received at least 14 days of study drug and had at least one post-dose efficacy measurement.		
Safety Analysis Set Population	Group of subjects who received at least one dose of study drug and had at least one post-dose safety assessment.		
PK population	PK sample collection of the first 6 subjects enrolled in the study.		
Serious AE	An AE occurring at any dose that: results in death; is a life-threatening experience; requires inpatient hospitalization or prolongation of an existing hospitalization; results in a persistent or significant disability/incapacity; or is a congenital anomaly/birth defect in the offspring of a patient who received study drug.		
Treatment- emergent AE	AEs occurring from the time of first dose through 7 days after the last dose or that is already present prior to the first dose of study drug and becomes more severe post-dose		

# **5** INTRODUCTION

## 5.1 Background

The purpose of this statistical analysis plan (SAP) is to outline in detail the statistical methods, data derivations, and presentations of data so that valid conclusions can be reached to address the study objectives outlined in the MN-001-NATG-201 protocol Amendment 3, dated 14 August 2017.

The planned analyses identified in this statistical analysis plan (SAP) may be included in regulatory submissions and/or future manuscripts. Exploratory analyses, not identified in this SAP, may be performed to support the clinical development program. Any post-hoc or unplanned analyses that are performed but not identified in this SAP will be clearly identified in the clinical study report (CSR).

## 5.2 Rationale

Preclinical and clinical studies have shown that MN-001 treatment improves lipid profile and protects the liver in patients with comorbidities of NASH or NAFLD and elevated serum triglyceride levels.

In an in vivo NASH mouse model, MN-001 (10, 30 and 100 mg) or placebo was administered to male mice for 3 weeks. MN-001 significantly reduced fibrosis in a dose-dependent manner (P < .01) as demonstrated by a reduction in liver hydroxyproline content, supporting MN-001's anti-fibrotic properties. MN-001 improved NASH pathology by inhibiting hepatocyte damage (P < .01) and ballooning (P < .01).

In a Phase 1 trial (Protocol no. MN-001-CL-003), the pharmacokinetics, safety, and tolerability of MN-001 at 750 mg BID vs 500 mg TID were evaluated in healthy volunteers. Additionally, sponsor conducted two Phase 2 trials to evaluate MN-001 in patients with asthma (Protocol no. MN-001-CL-001) and in patients with interstitial cystitis (MN-001-CL-002). Results from clinical laboratory assessments throughout these clinical trials , MN-001 showed a decrease in serum triglyceride levels, i.e., improvement, while subjects given placebo showed unchanged or increased serum triglyceride levels. These findings warranted a closer examination of MN-001's potential utility as a treatment for hypertriglyceridemia.

# **6 STUDY OBJECTIVES AND ENDPOINTS**

# 6.1 Study Objectives

# **Co-Primary Objectives:**

- To evaluate the effects of MN-001 on triglyceride levels in NASH and NAFLD subjects with hypertriglyceridemia;
- To evaluate the effects of MN-001 on Cholesterol Efflux Capacity in NASH and NAFLD subjects with hypertriglyceridemia.

# **Secondary Objectives:**

• To evaluate the safety and tolerability of MN-001;

- To evaluate PK profile of MN-001/MN-002 (metabolite) in first 6 enrolled subjects;
- To evaluate the effect of MN-001 on lipid profile
  - HDL-C, LDL-C, total cholesterol level;
- To evaluate the effect of MN-001/002 on liver enzymes;
- To evaluate the effect of MN-001/002 on percentage of fat in the liver assessed using MRI at Week 12.

### 6.2 Study Endpoints (Outcome Variable)

### **Co-Primary Outcome Variables**

• Mean change from baseline on serum triglyceride levels at Week 8

The primary endpoint is to evaluate the effects of MN-001 on serum triglyceride level in NASH and NAFLD with hypertriglyceridemia. The serum triglycerides will be measured as the difference after 8 weeks of treatment from pre-treatment serum triglyceride levels. Pre-treatment triglyceride level will be defined as the highest value of serum triglyceride at screening visit or baseline visit. The data are expressed as the percent change from the baseline value and calculated using he equation: Change = [100%\*(Endpoint value - Baseline Value)/Baseline Value]

• Mean change from baseline on cholesterol efflux capacity at Week 12

Cholesterol efflux capacity in the subjects will be quantified at National Institute of Biomedical Innovation, Osaka, Japan using the method previously reported (Ogura et al 2016). Percent efflux will be calculated by the following formula:  $[(\mu Ci of 3H-cholesterol in mediums containing 2.8% apolipoprotein B-depleted serum -\mu Ci of 3H-cholesterol in serum-free mediums)/\mu Ci of 3H-cholesterol in cells extracted before the efflux step] × 100. All assays will be performed in duplicate. To correct for inter-assay variation across plates, a pooled serum control from eleven healthy volunteers was included on each plate, and values for serum samples from patients were normalized to the value of the pooled sample in subsequent analyses.$ 

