#### **Summary Statistics**

Data will be summarized with respect to disposition, demographics, pre-treatment characteristics, safety outcomes, tolerability, and efficacy outcomes. Summary statistics for continuous variables will include the number of subjects, the mean, median, standard deviation, and range. For categorical data, summaries will include counts and percentages.

Biomarkers and clinical outcomes will be summarized longitudinally from baseline to Week 8 or Week 12, with means and standard deviations at each timepoint.

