#### 8.3 Precision

Results will be reported to 3 significant figures. Percentages will be reported to 0.1 percentage points. *P*-values will be reported to two digits when  $\geq$  .095, to three digits when  $\geq$  .00095 and < .095, and as < .001 for all smaller values.

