# **11 EFFICACY ANALYSIS**

### 11.1 Serum Triglyceride Level

The primary endpoint is to evaluate the effects of MN-001 on serum triglyceride level in NASH and NAFLD with hypertriglyceridemia. The serum triglycerides will be measured as the difference after 8 weeks of treatment from pre-treatment serum triglyceride levels. Pre-treatment triglyceride level will be defined as the highest value of serum triglyceride at screening visit or baseline visit. The data are expressed as the percent change from the baseline value and calculated using the equation: Change = [100%\*(Endpoint value - Baseline Value)/Baseline Value].

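### The triglyceride co-primary is titled and tabulated as a mean change but defined as a percent change, with no confidence interval and no named test

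*Combined protocol and SAP*

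**What the plan says.** SAP 6.2 names the co-primary "Mean change from baseline on serum triglyceride levels at Week 8". The text beneath it first describes a difference: "The serum triglycerides will be measured as the difference after 8 weeks of treatment from pre-treatment serum triglyceride levels". It then moves to a relative scale, as does SAP 11.1: "The data are expressed as the percent change from the baseline value and calculated using the equation", followed by 100% x (endpoint - baseline)/baseline. Protocol 10.1 uses the same formula. Table 14.2.1 returns to a mean change, and Listing 16.2.6.1 says only change.

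On summaries, the SAP's Summary Statistics paragraph states: "Summary statistics for continuous variables will include the number of subjects, the mean, median, standard deviation, and range". Biomarkers are also shown over time "with means and standard deviations at each timepoint". SAP 8.3 gives a rounding rule for P ("values will be reported to two digits when" and so on). Neither document names a test, a model, a transformation or a confidence interval for triglycerides.

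The denominator is set in SAP 6.2 and 11.1: "Pre-treatment triglyceride level will be defined as the highest value of serum triglyceride at screening visit or baseline visit".

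**The concern.** A mean change in mg/dL and a mean of individual percent changes are different estimands. A programmer working from the table title and one working from the formula would produce different primary results. Entry requires triglycerides above 150 mg/dL with no upper limit (Protocol 7.2.1), so a wide spread of starting values is allowed, and the two summaries can then diverge.

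Percent change is also bounded below at -100% and unbounded above. If a few subjects rise sharply, the arithmetic mean moves away from the change a typical subject shows. Protocol 13.1.3 and SAP 8.1 say the pilot's results are to inform the design of later studies. That use needs an effect on a declared scale, with its uncertainty.

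**Working it through.** **Inputs from the documents.** The percent-change formula (SAP 6.2, 11.1; Protocol 10.1). Sample size of about 20 (SAP 8.1) or about 40 (Protocol 13.1.3). Neither size comes with a power, effect or SD, so there is no calculation of the plan's own to reproduce. For a rough effect size, Protocol 4.2.1 gives Week 4 group means in the interstitial cystitis study: 100 x (109.5 - 136.1)/136.1 = -19.5%, and 100 x (106.7 - 135.7)/135.7 = -21.4% (printed as -21.3%). These are percent changes of group means, a third scale, so -20% is used below only as an illustration.

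**Assumptions.** R = Week 8 value / pre-treatment value is log-normal with geometric mean g and log-SD s between 0.3 and 0.5. Neither the shape nor s is in the documents.

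**1. The two scales can disagree in sign.** Take two constructed subjects, 160 to 200 and 800 to 700 mg/dL. Mean change: (40 - 100)/2 = -30 mg/dL. Mean percent change: (25 - 12.5)/2 = +6.25%.

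**2. Location.** The expected arithmetic mean percent change is 100 x (g x exp(s²/2) - 1).

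| s | exp(s²/2) | g = 0.8 (geometric -20%) | g = 1 (no geometric change) |
|---|---|---|---|
| 0.3 | 1.046 | -16.3% | +4.6% |
| 0.4 | 1.083 | -13.3% | +8.3% |
| 0.5 | 1.133 | -9.3% | +13.3% |

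**3. Precision.** The efficiency of the arithmetic mean ratio relative to the mean log ratio is s²/(exp(s²) - 1). This is 0.956, 0.922 and 0.880 at s = 0.3, 0.4 and 0.5, a loss of about 4%, 8% and 12%. Simulated 95% half-widths at n = 20 and g = 0.8, log-ratio against percent change, are 11.2 v 11.8, 14.9 v 16.4 and 18.8 v 21.8 points.

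**4. Power, as illustration only.** The SAP names no test, so a two-sided 5% one-sample t-test is assumed. With g = 0.8 and n = 20, the chance of showing a fall, log-ratio against percent change, is 88% v 75% (s = 0.3), 66% v 41% (0.4) and 47% v 22% (0.5). At n = 40 and s = 0.4 it is 93% v 63%. Most of the gap comes from the shifted target. At s = 0.4 and n = 20 the ratio of effect to half-width falls from 20/14.9 = 1.34 to 13.3/16.4 = 0.81. Shifting the target alone already takes it to 13.3/14.9 = 0.89.

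Steps 2 to 4 assume a pre-treatment value that was not selected for being high. The SAP's rule does select for that, so it needs its own check.

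**5. The highest-of-two rule with no drug effect.** Assume three independent log-normal readings per subject (two before treatment, one at Week 8), all variation within subject, and within-subject log-SD s/√2, so that a single-baseline log ratio has SD s. The larger of two log readings exceeds its mean by s/√(2π) on average. Hence:

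- Geometric change = 100 x (exp(-s/√(2π)) - 1) = -11.3%, -14.7%, -18.1% at s = 0.3, 0.4, 0.5.
- Arithmetic mean percent change = 100 x (2 exp(s²/2) Φ(-s/2) - 1) = -7.9%, -8.8%, -9.1%.
- Simulated chance of a significant false fall at n = 20: about 45% to 46% on log ratios, and 30%, 26% and 22% on percent change. At n = 40: about 77%, against 49%, 39% and 31%.
- With the mean of the two log pre-treatment values as the denominator, the expected log ratio is zero and the log t-test shows a false fall in about 2.5% of trials.

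**The case against.** The strongest reply is that the formula settles the scale. SAP 6.2 and 11.1 and Protocol 10.1 all define change as a percent, so the heading and table title can be read as shorthand. The sign reversal is a constructed two-subject case. The median is already planned, and under a log-normal model it estimates the typical proportional change directly. With n and SD reported, a reader can build an interval for the mean. The study is an uncontrolled descriptive pilot, its synopsis says the size does not rest on hypothesis testing, and a log-ratio in place of mean plus median is partly preference.

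Much of this stands. The percent-change reading is the more natural one, and the median is a real mitigation. What remains is that the title, the description as a difference and the table do not match the formula. The median has no interval, and the P-value format has no test behind it.

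Two stronger readings are tempting and not supported. A reader might infer that the plan biases the effect. It does not: the sample mean is unbiased for the mean percent change, which is simply a different estimand. Set against the geometric change it makes a fall look smaller, while the highest-of-two rule pushes towards an apparent fall. A reader might also infer that much of the precision is lost. Over the assumed range the loss is about 4% to 12%; the documents give no SD that would support more, and the power gap is mainly a change of target in a test the SAP does not contain.

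**Conclusion.** The point holds as one of scale and reporting, and the SAP should be changed. That the title and table disagree with the formula, that no interval is planned, and that P-values are formatted without a test can all be read directly from the SAP. The size of the gap between the arithmetic mean and the geometric change rests on assumed log-normal ratios: about -16% to -9% against -20% for a log-SD of 0.3 to 0.5. The power figures are illustrative only.

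A log-ratio analysis is an improvement only if the pre-treatment value is changed with it. Laid over the highest-of-two rule, it would enlarge a spurious fall and call it significant more often. The figures for that rule assume all variation is within subject.

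**What to change.** In SAP 6.2, SAP 11.1 and the title of Table 14.2.1, name percent change as the single scale and remove the wording that suggests an absolute difference. Then:

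- Set d = ln(endpoint TG / pre-treatment TG) and report 100 x (exp(mean d) - 1), with the 95% t confidence interval for mean d transformed the same way.
- Take any P-value from that same paired log analysis, and name the test and its sidedness.
- Keep the planned median and the arithmetic mean percent change as descriptive rows.
- Do not use the highest-of-two value in d. Use a pre-treatment value not selected for being high, such as the mean of the log pre-treatment values, and name the visits that supply it.

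This removes the selection made by the highest-of-two rule. It does not remove regression to the mean from the entry threshold of 150 mg/dL at screening, which a single-arm study cannot separate from a drug effect, so the report should say so.

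The cost is SAP wording, one table title and a few lines of code. No new data are needed.
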